This study will add affect-based physical activity goals to an existing mHealth intervention called MyDayPlan, which delivers morning and evening goal sessions. Every Sunday, participants receive a text message with a link to a brief REDCap questionnaire where they are asked about their tentative sleep and physical activity schedule for that upcoming week. On days participants have planned to do physical activity (according to the Sunday scheduling survey), they will engage in two goal sessions: one in the morning and one in the evening. Participants are alerted to complete a session with a text message that has a link to a REDCap form. Morning goal sessions provide an activity goal for the day (“goal module”); ask the participant to create a concrete plan for achieving this goal (“action plan module”); and prompt the participant to anticipate barriers and brainstorm solutions to accomplish the goal (“coping plan module”). Evening goal sessions have participants reflect on whether they were able to meet this goal (“self-monitoring module”). The focus of the goal module differs according to the participant’s assigned condition. For each condition, the Fitbit Versa smartwatch will feature a custom watch face with a clock (current local time), the date, current device battery levels, and a physical activity button. The physical activity button can be pressed whenever a subject wants to engage in physical activity, and provides real-time feedback on activity duration. If the subject’s moving average HR is too low following the physical activity button press, the Fitbit smartwatch will ask “Still exercising?” twice (options No; Yes) before auto-concluding the session. [Note: for the Comparison Study, the wording of this question will be “Still being physically active?”]. Participants will also have the option to view short explanatory videos throughout their participation that summarize aspects of what is expected of them in the study.

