Two enhancements (TYPE/CONTEXT and SAVOR) will augment the treatment effects. TYPE/CONTEXT provides tailored recommendations for activity types and contexts that satisfy personally important psychological needs (i.e., relatedness, social esteem, individual esteem, creativity, mindfulness/reflection, learning, challenge, entertainment/escapism, aesthetic appreciation, morality) as rated by each participant at baseline. Ratings from a crowdsourced panel of adults on Amazon Mechanical Turk will be used to determine the potential for specific activity types³⁹ and contexts to satisfy psychological needs; our tailoring algorithm will then recommend the corresponding activity type or context while accounting for reported constraints (e.g., ability, access). These details will be incorporated into a tailored recommendation provided to participants during the Sunday Scheduling survey. Specifically, the program will randomly select either type or context (i.e., location, audio, social) recommendations and will rotate every two weeks. For TYPE, participants’ top 3 activity types are displayed in the following message: “THIS WEEK, we recommend trying [top 3 activity types] because it will satisfy your unique needs and make the experience more enjoyable.” For CONTEXT, participants’ top 3 activity contexts are displayed in the following message: “THIS WEEK, we recommend trying a physical activity [top 3 activity contexts] because it will satisfy your unique needs and make the experience more enjoyable.” SAVOR implements a brief savoring exercise on the smartphone that takes place either after the planned physical activity session or during the evening goal session (after the self-monitoring module). Participants will respond to questions that are intended to enhance and prolong positive experiences during physical activity. To trigger attentional deployment, a common savoring strategy that involves intensifying experiences by focusing on them,^{40,41} participants will answer two open-ended prompts. These prompts are drawn from a prompt pool with

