EMA via Fitabase Engage: Real-time prompted EMA (“check-ins”) will be administered on the smartwatch using Fitabase Engage. If no interaction with the watch face is made, one reminder signal may be emitted before the prompt becomes inaccessible. EMA (“check-ins”) take approximately 30 seconds to complete. If a prompt occurs during an incompatible activity (e.g., driving), participants will be instructed to ignore it. To minimize participant burden, all questions are answered by tapping the smartwatch interface.^{46,47} **Three types of EMA (“check-ins”)**—random, event-contingent, and evening—will be sent to participants. Random and event-contingent are used for the Formative Study, while the Comparison Study will use event-contingent and evening. **Random EMA** (“check-ins”) will be randomly scheduled to be sent during normal waking hours, with a single prompt sent during each of four evenly spaced time windows: 0-4, 4-8, 8-12-, and 12-16-hours post-waking. Participants are asked to report their incidental affect via seven bipolar Likert Scale items. Five items (Energetic-Fatigued, Happy-Discouraged, Relaxed-Tense, Excited-Bored, Satisfied-Frustrated) are drawn from Russell’s Circumplex Model of Affect;⁴⁸ one (Good-Bad) represents core affective valence;⁴⁹ and one (Proud-Embarrassed) represents self-conscious emotion.⁵⁰ One of these seven items is repeated as a validity check (i.e., for a total of eight items). **Event-contingent EMA** (“check-ins”) are triggered when Fitbit sensors detect physical activity via moving average heart rate max. At least a 10-minute buffer (Formative Study) or 30-minute buffer (Comparison Study) separates the first and second event-contingent EMA during a single exercise bout, such that the moving average heart rate is “reset” following completion of the first prompt and the earliest possible second prompt is sent at least 10-minutes later (Formative Study) or 30-minutes later (Comparison Study) assuming the aforementioned threshold is met. A maximum of two event-contingent EMA will be sent within any given 60 min period. Participants are asked to safely pause their activity to answer questions about their **affective response (mediator)**^{49,51,52} with the same eight (i.e., 7 unique + 1 repeated) items as the random EMA above. Event-contingent EMA also include end a Rating of Perceived Exertion (RPE) item and end by asking whether the current physical activity is the participant’s planned session.⁵³ Finally, evening EMA (“check-ins”) are sent to participants at 8 pm local time every day and ask participants to report their feelings from that day using the same eight affective response items as the random and event-contingent EMA (only modified to ask about their overall affect from that day, rather than their current affect). A depiction of the daily intervention strategies and measures is shown in Figure 2.

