
Figure 2. Daily eMOTION Intervention and Prompting Schedule

Note. ^a Used in the Formative Study; ^b Used in the Comparison Study.

REDCap surveys during morning and evening goal sessions are scheduled to be sent at the same time every day: 5:00 AM with approximately 5 reminders sent once every hour (morning goal session), and 6:00 PM with approximately 5 reminders sent once every hour (evening goal session). Sessions are sent via text message and completed via REDCap. These sessions will deliver the intervention components, as discussed above. Morning goal sessions also assess **affectively-charged motivations (mediator)**⁵⁴ with one item from the Attraction-Antipathy subscale of the AFFEXX,⁵⁵ and **anticipated affect (mediator)** with another item.⁵⁶ The morning goal session also measures incidental affective states using the same 7 items as the random and event-contingent EMA, stress,⁵⁷ pain,⁵⁸ fatigue,⁵⁹ illness, and sleepiness⁶⁰ as key **situational factors (moderator)**. Finally, the participant is asked whether they want to set a physical activity plan for that day, and whether their plan from the day before is the same or different from the plan they want to set for that day. Evening goal sessions measure **physical activity type** and **context (covariates)** by asking participants to report characteristics about the physical activity they performed that day (e.g., running, dance, hiking, home, park, alone, with spouse, perceived exertion⁵⁸). They are also asked if they enjoyed the activity they did (if receiving affect-based goals) and whether they focused on their goal during physical activity. Three questions ask about the extent to which that day's physical activity satisfied various psychological needs.

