AIM 1: Determine whether affective mechanisms can be experimentally manipulated. In the Formative study, descriptive statistics (means, frequencies) will assess acceptability and feasibility of content, delivery methods, device usage, engagement, and raw values for change in affective mechanisms. The Comparison study will use an “intent to treat” approach to test the (1) within-subject effects of affect- vs. intensity-based goals (H1), (2) between-subject effects of affect-based goals with vs. without TYPE/CONTEXT (H2), and (3) between-subject effects of affect-based goals with vs. without SAVOR (H3) on the primary outcome (affective responses and affectively-charged motivations) and secondary outcome (physical activity). We will use random-effect regression models (level 1-days, level 2-subjects), which adjust for clustering within subjects and incorporate random effects.¹⁰⁷ Each treatment effect and each outcome will be tested in separate models. We will examine cross-level interactions between affect-based goals with vs. without savoring (level 2) and affective responses (level 1) to test H3.

AIM 2: Determine whether affective mechanisms mediate effects of interventions on physical activity (Comparison Study). Multilevel mediation will be tested using a 1-1-1 strategy that fits a set of simultaneous equations using path analysis in R.¹⁰⁸ Analyses will test the effects of intervention engagement on same-day/same-week affectively-charged motivations and affective response; the effects of affectively-charged motivations on same-day/same-week physical activity and the effects of affective responses on next-day/next-week physical activity; the indirect effects of intervention engagement on same- and next-day/same- and next-week physical activity via affective mechanisms (H4); and the total effects (mediated plus unmediated) of intervention engagement on physical activity.

AIM 3: Explore cross-person and cross-situation moderating effects (Comparison study). We will add interaction terms for time-varying and time-invariant effect moderators (H5).¹⁰⁹

Dissemination of Findings

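### AIM 2 relates undivided engagement to same-day motivation, which is rated before the bout, self-monitoring and SAVOR; an inert evening component can then appear to mediate

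*Combined protocol and SAP*

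**What the plan says.** H4 (section 2) and the AIM 2 analysis (Data Analysis, Comparison Study) use intervention engagement as a single exposure. For its link to the mediators, AIM 2 states: "Analyses will test the effects of intervention engagement on same-day/same-week affectively-charged motivations and affective response". The documents do not define engagement, split it by component or lag it.

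The timing of the pieces is given in section 5.

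- **Motivation.** "Morning goal sessions also assess affectively-charged motivations (mediator" (Instrumentation, REDCap surveys). The morning session is sent at 5:00 AM with about five hourly reminders.
- **Affective response.** Rated on the watch during the bout: "Participants are asked to safely pause their activity to answer questions about their affective response (mediator".
- **Self-monitoring.** "Evening goal sessions have participants reflect on whether they were able to meet this goal" (Intervention). The evening session is sent at 6:00 PM with about five hourly reminders.
- **SAVOR.** It "takes place either after the planned physical activity session or during the evening goal session". It is given in four of eight groups and only in the affect phase.
- **TYPE/CONTEXT.** Delivered in the Sunday scheduling survey.

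Of the morning and evening sessions together, the plan says "These sessions will deliver the intervention components, as discussed above". The paths from mediators to activity are given a time order in AIM 2: motivation to activity on the same day, affective response to activity on the next day.

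**The concern.** A cause must come before its effect. Motivation is rated in the morning, and on the design's own timetable the bout, self-monitoring and SAVOR follow. A same-day path from those behaviours to that rating runs backwards.

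Engagement is also chosen by the participant, not randomised. Self-monitoring and SAVOR both ask about that day's activity, so people may well complete them more often on days when they were active. Motivated mornings lead to active days, and active days lead to completed evening sessions. The same-day model then reads this chain in the wrong direction and finds that the evening component raised motivation, which in turn raised activity.

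H4 is the only hypothesis of Aim 2, and the trial's stated purpose is to identify mechanisms. A false mechanism claim is therefore the harm at stake, more than an error in minutes of activity.

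**Working it through.** **1. The plan's own figure.** The power paragraph gives f² = 0.04 and N = 200. For two equal groups d = 2√0.04 = 0.40, and n per group = 2(1.960 + 0.842)²/0.40² = 98.1, so 99 per group or 198 in all. The figure of 200 reproduces. It concerns H2 and H3. For H4 the plan gives only a level-1 size, 200 × 4 × 4 × 7 = 22,400, which is 112 days per person. Goal sessions are tied to planned activity days, whose number is not stated. I therefore use 3, 5 and 7 per week over 16 weeks: 48, 80 and 112 sessions.

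**2. Order of each possible exposure against that day's motivation rating.**

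| Exposure | Order |
|---|---|
| Morning session completed | Rating exists only if completed, so no variation |
| Morning goal and planning modules | Same session; order within it not stated |
| Activity button, goal focus during the bout | After the rating |
| Self-monitoring, SAVOR | After the rating |
| TYPE/CONTEXT on Sunday | Before the week's ratings |

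A score counting both sessions does not escape. Where motivation is observed, morning = 1, so (morning + evening)/2 = 0.5 + evening/2. After centring within person this is half the evening indicator: slope and standard error both double, and the t statistic is that of evening completion alone.

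**3. Size by hand, for an inert evening component.** All inputs are assumptions. Let activity log-odds rise 0.3 per SD of motivation, so motivation is about 0.3 SD higher on active days. Let completion odds double on active days. With about half of days active, the share of active days differs by about ln 2 × 0.25 = 0.173 between completed and missed evenings. The spurious path is about 0.3 × 0.173 = 0.052 SD; the simulated mean is 0.045 SD. With 60% completion the standard error is about 1/√(200 × sessions × 0.24).

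| Sessions | SE | 0.045/SE | Chance of p < .05 |
|---|---|---|---|
| 48 | 0.0208 | 2.16 | 58% |
| 80 | 0.0161 | 2.79 | 80% |
| 112 | 0.0136 | 3.31 | 91% |

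The motivation-to-activity path is real by assumption, so the first path decides. These figures run a little high, because differences between people in completion rate lower the within-person variance below 0.24.

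**4. Simulation.** 200 people, motivation autocorrelation 0.3, within-person-centred regressions with cluster-robust standard errors, 1,500 replicates; mediation is declared when both paths have p < .05.

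| Completion odds, active vs inactive day | 48 | 80 | 112 |
|---|---|---|---|
| 1 | 5% | 5% | 6% |
| 1.5 | 19% | 30% | 39% |
| 2 | 46% | 66% | 80% |

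Further runs with other person-effect and baseline settings gave 4-6%, 21-47% and 51-90% for the three rows. The result is sensitive to the link between motivation and activity:

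- At log-odds 0.1 per SD the rows become 4-5%, 7-9% and 10-16%.
- At 0.5 they become 4-7%, 44-79% and 87-99%.
- For SAVOR alone (100 recipients, 24-56 sessions, log-odds 0.3, doubled odds) the rate is 16-30%.

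If completion depends on motivation directly (motivation-to-activity slope 0.2 SD, 300 replicates), an odds ratio of only 1.05 per SD gives 57% at 48 days and 92% at 112. The spurious indirect effect is small: 0.09 minutes per session day at log-odds 0.3 and doubled odds, and 0.01-0.56 over all settings.

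**5. Lagged alternative.** Relating the evening component to the next session's motivation, adjusted for the earlier day's motivation and activity, brings false mediation to 4-7% in the setting of step 4. Lagging without adjustment is not enough: at 112 days and odds ratio 1.2 per SD of motivation it gives 5%, 94% and 100% at motivation autocorrelation 0, 0.3 and 0.5.

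Nor does the adjusted lag remove an unmeasured persistent day state. At state autocorrelation 0.3, 0.5 and 0.8 the rates are 8-9%, 11-12% and 27-30% when completion log-odds rise 0.1 per SD of the state, and 25-26%, 61-69% and 99-100% when they rise 0.3. The same-day model gives 96-100% throughout. Adding a morning measure of the state lowers the lagged rates to 4-8% and 7-36% at reliability 0.8, and to 6-18% and 14-87% at reliability 0.5.

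**The case against.** The strongest reply is that the plan never says engagement means evening completion. It could mean the morning modules, use of the activity button, or attention to the goal during the bout, which is reported in the evening but describes earlier conduct. This is right as far as it goes: the documents do not fix an evening-inclusive score. It does not rescue the same-day path to motivation. The button and goal focus also follow the morning rating, the modules share a session with it, and completion of that session cannot vary where motivation is observed. A graded score of the morning modules could vary, but nothing puts it ahead of the rating. Imputing missing motivation would give rows without a morning session, but the ratings there would come from the imputation model.

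A reader might go further and infer that all of AIM 2 runs backwards. The documents do not support that. Sunday TYPE/CONTEXT recommendations, morning modules before bouts, and both stated paths from mediators to activity are correctly ordered.

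Nor can one say that the path to affective response is reversed on most days. It is reversed only when the bout precedes the evening component or SAVOR, and no bout times are given. A bout may follow a completed evening session, and the evening check-ins "are sent to participants at 8 pm local time every day and ask participants to report their feelings from that day", so they may follow it too.

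Two further objections stand. Every magnitude rests on assumed inputs, and the rates run from nominal to near certainty. And the lag does not cure unmeasured confounding.

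**Conclusion.** The point holds for the same-day path from engagement to motivation. This is a stated rule that misorders time, not only a missing definition. A false finding of mediation also requires evening completion to depend on the day's activity or motivation; without that, the error rate is nominal. Under the assumptions shown, it is about 4-6% with no dependence, about 20-47% at 1.5 times and about 46-90% at twice the completion odds on active days. These figures show that the problem can be large; they do not estimate its size in this trial.

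For affective response the reversal is possible but of unknown frequency, so I give no size.

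A reader might also infer that the randomised comparisons are compromised. They are not: H1-H3 gain no false positives. For H3 the plan states no lag between affective response and motivation, and it states no same-day pairing either, so that is a request for clarification.

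This should be fixed before analysis. Confidence is moderate, because the mechanism is clear from the timetable and its strength is not.

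**What to change.** 1. Define engagement by component and by time of day.
2. Use morning-module engagement as the exposure for same-day bout affect and activity, not for motivation rated in the same session.
3. Relate bout-time and evening components on day t (including self-monitoring and SAVOR) to motivation at the next available morning session and to later affect and activity. Adjust for day-t motivation, affect and activity, and for the morning stress, pain, fatigue and affect items. These are already collected; for affect, "The morning goal session also measures incidental affective states using the same 7 items as the random and event-contingent EMA". Account for the length of the gap between sessions, since planned days are unevenly spaced.
4. Keep Sunday TYPE/CONTEXT engagement as an ordered same-week exposure. Report same-week paths for the other components as associations of mixed order.
5. Report H4 as non-randomised, and say that lagging does not remove confounding by unmeasured persistent day states.
6. As a minor clarification, state the H3 model as day-t affective response by SAVOR assignment, with next-available-morning motivation as the outcome.

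The cost is SAP wording and a re-timed data set; no new data are needed. At least one session per person and phase is lost, which is 1/56 = 1.8% at seven sessions a week over eight weeks and 1/24 = 4.2% at three, and more where sessions are missed. The lagged affect path also needs a later bout, so it uses fewer rows.

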The exploration of how and why certain treatment components bring about desired changes is a crucial step that has previously been overlooked. While later-stage interventions are well-positioned to address efficacy, they leave many unanswered questions about underlying behavior change mechanisms—resulting in limited generalizability and a field-wide replication crisis.¹¹ Early-stage intervention development studies are needed to elucidate theoretical components that determine why certain interventions are successful—and why others fail.

2. Purpose/Objectives/Aims/Research Questions

In response to these research gaps, the present study will examine whether affective mechanisms (1) can be experimentally manipulated in real-world settings; and (2) mediate the relationship between interventions and physical activity behavior. As an ORBIT model phase 1 trial, the research will begin with a 3-week Formative study to assess acceptability and feasibility of a novel physical activity intervention in adults with increased risk for cancer. A 19-week Comparison study will then test the intervention to achieve the following aims.

AIM 1: Refine and optimize treatments to experimentally manipulate affective mechanisms in real-world settings.

H1: Within-subjects, positive affective responses and affectively charged motivations, and physical activity will be higher in the affect-based (vs. intensity-based) condition.

H2: Between-subjects, positive affective responses and affectively charged motivations, and physical activity will be higher in the affect-based condition with TYPE/CONTEXT (vs. without TYPE/CONTEXT).

H3: Between-subjects, the association between affective responses and affectively charged motivations will be stronger, and physical activity will be higher in the affect-based condition with SAVOR (vs. without SAVOR).

AIM 2: Determine whether affective mechanisms mediate effects of treatments on physical activity.

H4: Within-subjects, affective response and affectively charged motivations will mediate associations between intervention engagement and physical activity at the day-/week-level in all conditions of the Comparison study.

AIM 3: Explore cross-person and cross-situation moderating effects.

H5: The above Comparison study effects will be larger among individuals with lower self-regulatory capacity (e.g., self-control, self-efficacy) and on days with more situational constraints (e.g., incidental stress, pain).

3. Participants (sample)

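### Aim 2 asks whether affect mediates the treatment effects, but the only planned mediation model takes undefined intervention engagement as its exposure, so no indirect effect of a randomised contrast is planned

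*Combined protocol and SAP*

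**What the plan says.** The objectives section states the aim as "AIM 2: Determine whether affective mechanisms mediate effects of treatments on physical activity". The Data Analysis section repeats it with interventions in place of treatments. The study purpose is put the same way: whether affective mechanisms mediate between the interventions and activity.

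H4, the only hypothesis under Aim 2, says that affective response and affectively charged motivations "will mediate associations between intervention engagement and physical activity at the day-/week-level", within subjects and in every condition of the Comparison Study.

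The Aim 2 analysis is a 1-1-1 multilevel path model. Its first step reads "Analyses will test the effects of intervention engagement on same-day/same-week affectively-charged motivations and affective response". It then estimates "the indirect effects of intervention engagement on same- and next-day/same- and next-week physical activity via affective mechanisms (H4"), and finally the total effect, again of engagement. Motivation is related to same-day or same-week activity, and affective response to next-day or next-week activity.

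The randomised contrasts (affect- versus intensity-based goals, with or without TYPE/CONTEXT, with or without SAVOR) are analysed by intention to treat under Aim 1, where "Each treatment effect and each outcome will be tested in separate models". For SAVOR the plan adds: "We will examine cross-level interactions between affect-based goals with vs. without savoring (level 2) and affective responses (level 1) to test H3". This matches the part of H3 which holds that with SAVOR "the association between affective responses and affectively charged motivations will be stronger".

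**The concern.** The aim is about treatments and the model is about engagement. Engagement cannot be read as another name for assigned condition, because H4 applies it within every condition. The phrase occurs only in H4 and the Aim 2 analysis paragraph. The Instrumentation section labels an outcome, mediators, moderators and covariates, but no engagement variable, data source or day/week scoring rule.

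The trial randomises 360 people to eight sequence-by-enhancement groups to learn how the components work. If the plan is followed, the mechanistic question has no randomised answer, although the data for one are planned. What is estimated instead is a path from participants' behaviour after randomisation, which randomisation does not protect.

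The missing definition matters in its own right. Motivation is measured in the morning goal session. Setting a plan, pressing the activity button or completing a savoring exercise could each count as engagement, and some of these come after that measurement. The order of exposure and mediator is therefore not fixed.

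**Working it through.** **1. Exposures side by side.**
- Aim 2 (objectives and analysis section): treatments or interventions.
- H4: engagement, in all conditions, worded as associations.
- Aim 2 model: engagement in the path to the mediator, the indirect effect and the total effect.
- Aim 1 models: randomised condition, on mediator and outcome separately. Two separate effects are not an estimate of an indirect effect.

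Affect versus intensity goals varies within person in the crossover, so it could be the exposure of a 1-1-1 model; the text does not say so. TYPE/CONTEXT and SAVOR vary between persons (level 2) and cannot be a 1-1-1 exposure.

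**2. The plan's own power figure.** f² = .04 gives d = 2√.04 = 0.4. A two-sided t-test at alpha .05 with 100 per level has power 80.4%, which reproduces the stated N = 200. N = 360 less 30% leaves 252, or 126 per factor level, with power 88.5% (71.8% at alpha .01). For H4 the plan gives only a day-level count, 200 × 4 × 4 × 7 = 22,400 (112 days per person), and no size for an indirect effect.

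**3. Possible bias in the engagement model (assumed settings).** Same-day motivation path only, no adjustment, all true effects zero. A daily state u ~ N(0,1) acts with coefficient k on binary engagement, motivation and activity, each with unit-variance error.
- Path to mediator: a = 2√(2/π)·k²/√(1+k²).
- Mediator to outcome given engagement: b = k²v/(1+k²v), where v = 1 − (2/π)k²/(1+k²).

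| k | a | b | false a·b | significant, 200 × 112 days |
|---|---|---|---|---|
| .1 | .016 | .010 | .0002 | about 1% |
| .2 | .063 | .038 | .0024 | about 99% |
| .3 | .138 | .079 | .011 | 100% |
| .5 | .357 | .179 | .064 | 100% |

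The last column is simulated (200 runs, person-mean-centred regressions, Sobel test).

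**4. A randomised exposure under the same state.** With no effect of condition on the mediator, false indirect effects appeared in 5/5/7% of runs at k = .2/.3/.5, about the nominal level. With a real a = .1 SD and b = 0, the false indirect effect is .1·k²/(1+k²) = .004/.008/.020 SD, significant in every run. Randomisation protects the first path but not the second.

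**5. Power of the randomised indirect effects (assumed values, unit SDs).**
- *TYPE/CONTEXT*, joint test, 252 people: power ≈ (a-path power) × Φ(b√252 − z). At alpha .05 and b = .1/.2/.3: .885 × .355/.888/.997 = 31/79/88%. At alpha .01: .718 × .161/.725/.986 = 12/52/71%. Simulation gives 32/78/88% and 12/51/70%.
- *Condition, path to mediator*, a = .05 SD, person-level SD of the effect .2, T observed days per phase: SE = √[(.2² + 2/T)/252]. T = 56: SE = .0173, power 82%. T = 24: SE = .0221, power 62%, or 38% at alpha .01.

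Alpha .01 is Holm's first step if five indirect effects share one family (.05/5): two contrasts by two mediators, plus one SAVOR index.

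**The case against.** The strongest reply is that H4 is Aim 2's only hypothesis, speaks of associations, and is tested as written; an early-phase study may narrow a broad aim in this way. The first part stands: the model fits H4. It does not close the gap, because the aim and the stated purpose still ask about treatment effects. Narrowing the aim is a legitimate alternative, provided it is done openly.

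A reader might infer that the engagement model is bound to produce false mediation, given the near-certain significance at k = .2. The documents do not support that. Every k is assumed, the false effect at k = .2 is only about .002 SD, and at k = .1 there is no problem. Adjustment could shrink it further: the plan's p < .10 rule may admit the morning items. Their use in the mediation paths is not fixed in advance, however, and stress, pain, fatigue, illness and sleepiness are labelled moderators. Nor do the rates carry over to the affective-response path, which is lagged to the next day or week. If engagement meant completing the morning session, motivation would be unobserved on non-engaged days, and the simulated data would not exist in that form.

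A reader might also infer that a randomised exposure makes the mediation causal. Step 4 shows otherwise: at k = .2 its bias (.004) exceeds that of the engagement model (.002), though it is smaller at .3 and .5. In addition, affective response is collected only when the watch detects activity, so even its first path is not fully protected.

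Finally, how far engagement reflects participant choice is itself an inference about an undefined variable. Sessions tied to days on which the participant planned activity, and the daily question on setting a plan, point that way; the randomly generated goals do not.

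**Conclusion.** The concern holds as a mismatch between aim and analysis. No indirect effect of any randomised contrast is planned, and the exposure that is used is not operationalised. This rests on the text and on no simulation. H4 can support a statement about association with engagement, not the conclusion Aim 2 announces. Aim 1's randomised tests are unaffected.

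The size of any confounding bias is not established. Under the assumed settings it runs from negligible to .064 SD without adjustment, on the same-day motivation path only. The change should be made before analysis, with modest expectations: power for the randomised indirect effects is adequate only for favourable assumed values.

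**What to change.** 1. **Add a mediation model with assigned condition as exposure.** Make affect versus intensity goals the main one (1-1-1, adjusted for period), with the plan's lags and one named activity outcome. As secondary analyses add TYPE/CONTEXT (2-1-1, affect phase) and, to match H3, SAVOR as moderator of the path from affective response to motivation. State the multiplicity rule.
2. **Keep the engagement model for H4 and report it as associational.** Define engagement from components that precede the mediator. Adjust only for variables measured before that component, such as prior-day activity and affect where they precede it. Use the morning items only where they come first; otherwise adjusting for them can remove the effect under study.
3. **For every mediation model, add a sensitivity analysis** stating how strong mediator-outcome confounding must be to remove the indirect effect. Report by condition the share of days with no affective response.
4. **If no randomised model is added,** reword Aim 2 and its conclusions to association with engagement.

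The cost is SAP wording and a few models on data already planned; no new collection or sample is needed. Given the power in step 5, report the randomised indirect effects as estimates with confidence intervals, and do not read a non-significant one as absence of mediation.
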